3.1. Visit Windowing

Subjects do not always strictly adhere to the visit schedule timing in protocols. Therefore, the designation of visits (or timepoints) will generally be based on the actual day of evaluation relative to the date of first dose of study treatment (Day 1), rather than the nominal visit, for analyses conducted by visit.

Mutually exclusive visit windows containing no gaps will generally be utilized to assign visits for by visit analysis and will correspond to post-baseline visits specified in the protocol. Visits for analysis will be assigned by using a windowing scheme as described below.

The upper bound of the baseline visit window is Day 1, and the lower bound of the first postbaseline visit window is Day 1 after the time of the first dose. For all other lower and upper bounds of visit windows, windows will end at the midpoint between scheduled visit timepoints, with the midpoint in the latter visit window with the exception of the Week 24 visit for the efficacy endpoints, which will include Day 174 as the upper bound of the visit window.

If a subject's last observation is after the date of first dose of study treatment but prior to the first scheduled visit, data from an early withdrawal visit will be assigned to the first scheduled visit. If two or more evaluations occur in the same visit window, the evaluation closest to the target visit day will be selected for inclusion in the analysis. If multiple evaluations are equally close to the target visit day, then the latest evaluation will be selected for inclusion in the analysis. The target visit day for Week 2 and on is defined as the week number specified in the SoA of the protocol multiplied by 7 plus 1.

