
 • Immediately discontinue IP • Report the event to the Medical Monitor within 24 hours • Complete the liver event eCRF and complete an SAE data collection tool if the event also met the criteria for an SAE^b • Perform liver chemistry follow-up assessments • Monitor the subject until liver chemistry test abnormalities resolve, stabilize, or return to baseline (see MONITORING) • Do not restart/rechallenge subject with IP unless Medical Monitor approval is granted • If restart/rechallenge not granted, permanently discontinue IP and continue subject in the study for any protocol specified follow up assessments 
MONITORING:
 
 • Repeat liver chemistry tests (include ALT, AST, GGT, alkaline phosphatase, total bile acids, bilirubin, and INR) and perform liver event follow-up assessments within 24 hours • Monitor subject twice weekly until liver chemistry test abnormalities resolve, stabilize, or return to baseline • A specialist or hepatology consultation is recommended 	
Additional Liver Panel
 
 • Viral hepatitis serology^d • Obtain INR and recheck with each liver chemistry assessment until the ALT and/or AST values show downward trend • Obtain blood sample for pharmacokinetic (PK) analysis • Serum creatine phosphokinase (CPK) and lactate dehydrogenase (LDH) • Fractionate bilirubin, if total bilirubin > 2x ULN • Obtain complete blood count with differential to assess eosinophilia • Record the appearance or worsening of clinical symptoms of liver injury, or hypersensitivity, on the adverse event (AE) report form • Record use of concomitant medications (including acetaminophen, herbal remedies, and other over-the-counter medications) on the concomitant medications eCRF • Record alcohol use on the liver event alcohol intake eCRF • Anti-nuclear antibody, anti-smooth muscle antibody, Type 1 anti-liver kidney microsomal antibodies, and quantitative total immunoglobulin G (IgG) or gamma globulins • Serum acetaminophen assay • Liver imaging (ultrasound, magnetic resonance, or computerized tomography) and/or liver biopsy to evaluate liver disease

^a Serum bilirubin fractionation should be performed if testing is available. If serum bilirubin fractionation is not immediately available, discontinue IP if ALT or AST \geq 3x ULN **and** bilirubin > 2x ULN. Additionally, if serum

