Dates in by-subject data listings will be displayed as yyyy-mm-dd (e.g., 2015-01-24). In general, by-subject data listings will be sorted by randomized treatment group and subject number.

Disposition, demographic and baseline characteristics, significant protocol deviations, and prior medication tables will be presented by randomized treatment group and will also include an overall column combining all treatment groups. Efficacy tables will be presented by randomized treatment group only. Safety tables will be presented by actual treatment group and, in general, will also include a total GB001 column combining all GB001 treatment groups. Sorting in disposition, etc. tables will be based on decreasing incidence within the overall column. In general, AE tables that are displayed by system organ class (SOC) and/or preferred term (PT) will be sorted by the internationally agreed order for SOC, and by decreasing incidence and then

alphabetically for PT within the total GB001 column. Otherwise, safety tables when applicable, will be sorted by decreasing incidence within the total GB001 column.

Assessments at the Randomization Visit are to be performed prior to the first dose of study treatment. Therefore, for all measures, the baseline value is defined as either the last non-missing value on or before the first dose of study treatment or the mean over the last 7 days of the Run-in including the value on Day 1.

If multiple evaluations occur on the same day, the average of these evaluations will be used for analysis excluding maximum post-baseline, abnormality, and outlier analyses.

If complete dates are unavailable, July 2 (midpoint of a non-leap year) will be utilized in calculations in cases where both month and day are missing, and the 15th will be utilized in calculations in cases where only day is missing.

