9.2. Clinical Laboratory Evaluation

Actual values and change from baseline values for quantitative laboratory parameters (clinical and liver chemistry, hematology, and urinalysis) will be summarized by visit for the safety population.

Shift tables will be presented for clinical and liver chemistry and hematology parameters summarizing shifts from baseline to high and low at any time post-baseline based on laboratory normal ranges. A shift table will also be presented for urinalysis parameters summarizing shifts from baseline to positive at any time post-baseline based on laboratory normal ranges.

A summary of maximum post-baseline values > 1.0, > 1.5, and > 3.0 GI/L for blood eosinophils will be presented.

Summaries of maximum post-baseline values for liver chemistry parameters (alanine aminotransferase [ALT], aspartate aminotransferase [AST], concurrent ALT/AST and total bilirubin, total bilirubin, direct bilirubin, indirect bilirubin, alkaline phosphatase, and gamma-glutamyl transferase [GGT]) according to categories based on multiples of upper limit of normal (ULN) will be presented. Liver chemistry parameters according to categories based on multiples of ULN will also be presented by visit.

For laboratory shift tables and summaries of maximum post-baseline values, only subjects with at least one post-baseline value will be included.

The time to first elevation for ALT will be presented for subjects with an elevation in ALT. An elevation for ALT will be defined as the first post-baseline value $\geq 1.5 \text{ x}$ ULN for subjects with a baseline value \leq ULN, and the first post-baseline value with a > 50% increase from baseline for subjects with a baseline value > ULN. This analysis will also be repeated using a threshold of > 1.0 x ULN. In addition, the time to first elevation of AST will be summarized in the same manner as described above for time to first elevation of ALT.

In addition, the following figures/plots will be provided:

- Mean change from baseline values, including SE bars, by visit figures for liver chemistry parameters
- Mean ratio of actual values to ULN, including SE bars, by visit figures for liver chemistry parameters
- Evaluation of Drug-Induced Serious Hepatotoxicity (eDISH) (Merz, 2014) plots
- Mean actual values and mean change from baseline values, including SE bars, by visit figures for blood eosinophils
- Maximum post-baseline values versus baseline values plot for blood eosinophils

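### The by-visit liver table in multiples of ULN keeps only the value nearest the target day, so it can understate when elevations of >= 3x and >= 5x ULN occur by dose; the peaks remain in other planned outputs

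*SAP*

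**What the plan says.** SAP 3.1 assigns results to visits by the actual study day, "rather than the nominal visit, for analyses conducted by visit". Unscheduled tests therefore fall into the windows together with scheduled ones. On the bounds: "windows will end at the midpoint between scheduled visit timepoints, with the midpoint in the latter visit window". Where a window holds two or more results, "the evaluation closest to the target visit day will be selected for inclusion in the analysis", and a tie goes to the later one.

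SAP 9.2 then plans the table at issue: "Liver chemistry parameters according to categories based on multiples of ULN will also be presented by visit". It names no worst-value rule for it. It does not list the category cut-offs either; this point uses 3x and 5x ULN because those are the ALT/AST action thresholds in Protocol Appendix 6, Tables 4 and 5.

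SAP 3 has an exception for extreme-value analyses, but it concerns several results on one day: "the average of these evaluations will be used for analysis excluding maximum post-baseline, abnormality, and outlier analyses". No matching exception exists for several results in one window.

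Protocol Appendix 6 sets the extra testing. ALT or AST above 1x and below 3x ULN is confirmed within 24 to 48 hours, and further monitoring is agreed with the Medical Monitor. Table 4 asks for a repeat within 24 to 48 hours and then at least weekly tests. Table 5 asks for a repeat within 24 hours, and then: "Monitor subject twice weekly until liver chemistry test abnormalities resolve, stabilize, or return to baseline".

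**The concern.** Appendix 6 produces clusters of liver results in the subjects whose enzymes are rising, and the window rule keeps one result from each cluster without regard to its height. Repeat testing starts at anything above 1x ULN. The retained scheduled draw may therefore be only mildly raised while a later 3x or 5x result in the same window goes unused.

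Protocol 2.3.1 names drug-induced liver injury as a potential risk, on the basis of two Hy's Law cases, one of them in this still-blinded study. Protocol Appendix 14 records that liver tests at Weeks 1 and 3 were added to strengthen monitoring in the first month. Timing by dose is thus a question the liver outputs should answer. For elevations of 3x ULN or more, only the by-visit table answers it in aggregate.

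**Working it through.** There is no plan figure to reproduce: neither document states an expected count or an ALT time course.

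**Windows.** The target is 7 x week + 1, and a midpoint day goes to the later window. SAP 3.1 states targets only from Week 2 ("The target visit day for Week 2 and on is defined as the week number"); Day 8 is assumed for Week 1. Liver visits come from the Schedule of Activities.

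- Week 2: Days 12-18 (7 days). Week 3: Days 19-25 (7 days). Week 4: Days 26-42 (17 days).
- Weeks 8, 12, 16, 20 and 24: Days 43-70, 71-98, 99-126, 127-154 and 155-182 (28 days each; the Day 174 cap is for efficacy endpoints).

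Twice-weekly testing can put 4 x 2 = 8 results in a 28-day window. One is kept.

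**Worked example (assumed values).** Day 57 = 3.2, Day 59 = 4.1, Day 62 = 6.0, Day 66 = 4.0 and Day 69 = 2.5 x ULN. All lie in the Week 8 window, whose target is Day 57. The by-visit table keeps 3.2, so the subject counts at >= 3x but not at >= 5x. The maximum post-baseline table shows 6.0.

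**Direction.** The highest value in a window cannot be below any one value selected from it. Each by-visit count is therefore at most the worst-in-window count.

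**Size, first assumed curve.** Let the value d days from a peak P be 1 + (P - 1) x 0.5^(d/h), with h the half-life of the excess in days. It reads below 3x ULN when d > d* = h x log2((P - 1)/2). If the peak is uniform within W days either side of the target, the share read below 3x on the target day is 1 - d*/W (0 if negative). At P = 5 and h = 7, d* = 7 and the share for W = 14 is 1 - 7/14 = 50%.

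| Peak | d* (h = 5 / 7 / 10) | 28-day window, W = 14 | 7-day window, W = 3.5 |
|---|---|---|---|
| 4x | 2.9 / 4.1 / 5.8 | 79 / 71 / 58% | 16 / 0 / 0% |
| 5x | 5.0 / 7.0 / 10.0 | 64 / 50 / 29% | 0 / 0 / 0% |
| 8x | 9.0 / 12.7 / 18.1 | 35 / 10 / 0% | 0 / 0 / 0% |

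These figures are for the 3x cut-off and treat the peak itself as measured. At any cut-off, a peak only just above the line can be missed whatever the window length.

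**Size, second assumed curve, with triggered testing.** Bell-shaped rises on a baseline of 0.6x ULN; SD 5, 10 or 20 days; median peak rise 3x or 5x ULN (log-normal, SD 0.6); peak uniform over Days 10-165; scheduled draws within 2 days of target. After a result above 1x ULN, the repeat comes at 2 days and then every 7 days, or every 3 days at 5x and above. There were 3,000 simulated subjects per setting. Only sampled values count. Entries are subject-visit cells, closest value / highest value.

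| SD, median rise | >= 3x | Fewer | >= 5x | Fewer |
|---|---|---|---|---|
| 5, 3x | 935 / 1380 | 32% | 272 / 475 | 43% |
| 5, 5x | 1591 / 2391 | 33% | 792 / 1364 | 42% |
| 10, 3x | 1957 / 3130 | 37% | 607 / 1116 | 46% |
| 10, 5x | 3248 / 4900 | 34% | 1611 / 2824 | 43% |
| 20, 3x | 3591 / 4788 | 25% | 1156 / 1729 | 33% |
| 20, 5x | 6212 / 7953 | 22% | 3246 / 4483 | 28% |

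Of the subjects whose sampled maximum reached 5x, the share appearing in no >= 5x by-visit cell ran from 1 - 1642/1779 = 8% (SD 20, 5x) to 1 - 243/393 = 38% (SD 5, 3x).

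**Other outputs.** The maximum table and the any-time shift tables show that a peak occurred, by treatment group, but collapse over time. Time to first elevation is set at 1.5x ULN, or more than 50% above an already raised baseline, and repeated at 1.0x; it is never run at 3x or 5x. Mean figures dilute individual peaks. Listings show timing subject by subject, not in aggregate.

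**The case against.** The strongest reply is that nothing is hidden. SAP 9.2 plans "Summaries of maximum post-baseline values for liver chemistry parameters", including concurrent ALT/AST and total bilirubin, together with eDISH plots, any-time shift tables and listings. None is described as a by-visit analysis, so the window rule does not reach them. That stands. A reader might infer that peaks are dropped from the liver analysis or that a safety signal would be missed; the documents do not support that.

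Second, a by-visit table may be meant to show status near each visit, so calling its counts wrong presumes a different purpose. This stands in part. Equal to or below the worst-in-window counts is the accurate description. But the SAP does not state that purpose, and a reader will see by-visit counts that need not agree with the maximum table in the same section.

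Third, the retained value is often the scheduled draw that triggered the repeats, so the subject still shows as raised. True, but possibly in a lower category, because repeats start above 1x ULN.

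Fourth, the sizes rest on invented curves, and the first curve counts peaks before the target draw that might never have been sampled. That stands against the first table. The second counts sampled values only, but its curves are assumed too.

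Finally, the highest value per window favours frequent testing: a subject tested more often has more chances to enter a high category. That is a genuine cost.

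**Conclusion.** The point holds for one table. As written, by-visit liver counts at >= 3x and >= 5x ULN are equal to or below the worst-in-window counts, and that table is the only planned aggregate display of when such elevations occur by dose. The direction follows from the rules alone. The size does not: 22-37% fewer cells at >= 3x and 28-46% fewer at >= 5x are results of the assumed curves, not forecasts. The loss can be material in the 28-day windows from Week 8 on. At 3x it is small in the 7-day windows at Weeks 2 and 3, so the argument should not lean on the added Week 3 visit.

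Two further inferences go too far. The loss is not certain for every subject with an elevation. Nor is it confined to the GB001 arms: placebo subjects with elevations are treated the same way, although an arm with more elevations has more to lose. No efficacy result or stopping decision is shown to depend on this table.

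**What to change.** Add to SAP 3.1 or 9.2 that by-visit liver ULN-category tables use the highest value in each window, including unscheduled central-laboratory results. Grade any local-laboratory result against its own ULN and flag it, since SAP 3.3 already contemplates laboratory analyses with and without local values. Keep the closest-to-target rule for by-visit means and figures.

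Footnote the table to say that subjects tested more often have more chances to enter a high category. The same edit can supply the target day for the Week 1 liver visit, which SAP 3.1 leaves unstated.

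The cost is a sentence, a footnote and one derived record flag. The maximum post-baseline table does not change.

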3.2. Standard Calculations

Standard calculations are described as follows:

Age:

Age will be calculated in years to two decimal places using the date of birth and the date of the Screening Visit (Visit 1), rounded down to the nearest integer.

Duration:

Duration between two dates date1 and date2 will be calculated as follows:

date2 - date1 + 1, when expressed in days

(date2 - date1 + 1)/7, when expressed in weeks

(date2 - date1 + 1)/365.25, when expressed in years

Change/Percent Change from Baseline:

Change from baseline will be calculated as: Value at post-baseline visit - value at baseline

Percent change from baseline will be calculated as: (Change from baseline/value at baseline) \ast 100%

Note: Change from baseline summaries will only include subjects with a baseline value and at least one post-baseline value. If the value at baseline is 0, percent change from baseline will be missing.

Study Day:

Study day will be calculated as follows:

assessment date – date of the first dose of study treatment, where assessment date < date of the first dose of study treatment

assessment date – date of the first dose of study treatment + 1, where assessment date \geq date of the first dose of study treatment

3.3. Considerations Related to the COVID-19 Pandemic

Screening of subjects for this study began in October 2018, and the last subject is expected to complete their participation in the study around August-September 2020. As such, a portion of this study's conduct may be affected by the global Coronavirus Disease 2019 (COVID-19) pandemic.

At the time of finalization of this SAP in April 2020, several regulatory authorities have recently issued guidance related to trial conduct and associated methodological issues related to the effect of the COVID-19 pandemic, including Food and Drug Administration (FDA) (Reference: FDA Guidance on Conduct of Clinical Trials of Medical Products during COVID-19 Pandemic, March 2020) and European Medicines Agency (EMA) (References: Guidance on the Management of Clinical Trials during the COVID-19 (Coronavirus) pandemic, Version 2 (27/03/2020) and Points to consider on implications of Coronavirus disease (COVID-19) on methodological aspects of ongoing clinical trials, 25 March 2020).

Potential anticipated effects on conduct of this ongoing study related to the COVID-19 pandemic include, but are not limited to, the following: subject discontinuation of study treatment and/or withdrawal from study; inability or reduced ability for subjects to continue on IP due to disruptions in IP dispensing; missed visits; alternative procedures (e.g., telephone visit or virtual visit) used for collection of critical efficacy and/or safety assessments; and inability for sites to complete entry of data in the electronic case report form (eCRF) and/or collect data via other sources (e.g., eDiary).

At the time of finalization of this SAP, it is acknowledged that it is not known the degree to which study conduct and subject participation may be affected by the COVID-19 pandemic, as the study is currently approximately 4-5 months from the last subject completing participation.

Given the COVID-19 pandemic is a developing and rapidly evolving situation, a determination will be made at the end of study if additional statistical analyses are warranted as part of the final analysis, should participation of subjects be affected by the COVID-19 pandemic to a substantial degree. These additional analyses would be undertaken to enable an understanding of the potential impact of the COVID-19 pandemic on study results.

A non-exhaustive list of examples of such additional analyses is as follows:

- Analysis of compliance:
 - By subgroup of subjects who received direct IP shipment due to the COVID-19 pandemic versus those that did not
- Analyses of primary and select secondary efficacy endpoints:
 - By subgroup of subjects whose study participation was affected by the COVID-19 pandemic versus was not affected;
 - Excluding only data that is missing for reasons related to the COVID-19 pandemic (but including imputation of data missing for other reasons); and
 - By subgroup of subjects who had an alternative method of collection for an assessment contributing to a particular endpoint (e.g., ACQ-5 completed by subject at home via virtual visit) versus subjects who did not have an alternative method of collection
- Analysis of AEs:
 - Incidence of AEs by subgroup of subjects whose study participation was affected by the COVID-19 pandemic versus was not affected;
 - Incidence of AEs that were collected via an alternative method versus incidence of AEs that were not collected via an alternative method
- Analysis of laboratory values:
 - By subgroup of subjects whose study participation was affected by the COVID-19 pandemic versus was not affected;
 - Excluding values resulting from local collection due to reasons related to the COVID-19 pandemic; and
 - Including only values resulting from local collection due to reasons related to the COVID-19 pandemic

In addition, by-subject listings indicating subjects whose study participation was affected by the COVID-19 pandemic, subjects with missing data related to the COVID-19 pandemic, and/or subjects with an alternative method of collection for specific assessments may be provided.

4. ANALYSIS POPULATIONS

4.1. All Enrolled Population

The all enrolled population will include all subjects with a non-missing date of informed consent. The all enrolled population will be utilized for disposition summaries.

4.2. **Run-in Period Population**

The run-in period population will include all enrolled subjects who are not screen failures and enter the Run-in period. The run-in period population will be presented in disposition summaries.

4.3. Intent-to-Treat Population

The intent-to-treat (ITT) population will include all subjects who are randomized and receive at least 1 dose of study treatment, with subjects grouped according to randomized treatment. The ITT population will be utilized for efficacy analyses.

4.4. **Per Protocol Population**

The per protocol population will include all subjects in the ITT population who do not violate terms of the protocol that may affect primary or secondary efficacy outcomes. The criteria for the per protocol population will be determined and documented prior to unblinding based on review of study data in a blinded manner.

Programmatically-derived and/or manually reviewed criteria for exclusion from the per protocol population include, but are not limited to:

- Subjects who do not meet the following eligibility criteria:
 - Inclusion Criteria 5, 6, 7, or 9
 - Exclusion Criteria 12
 - Randomization Criteria 1, 2, 4, 5, or 11
- Poor study treatment compliance up to the last dose of study treatment defined as < 80.0% compliance
- Subjects at any site with good clinical practice (GCP) compliance issues identified, if applicable

